Objectives: To determine if a hyperosmolar solution, similar to what is used in head trauma patients, can reduce the degree of fluid extravasation in knee arthroscopy. To determine if a hyperosmolar solution has any effect on post-operative knee pain compared to the standard isotonic solution. To determine if a hyperosmolar solution has any effect on post-operative pain medicine consumption compared to the standard isotonic solution.

Contribution: The potential benefits of this study lie in determining the differences noted in our shoulder arthroscopy clinical trial extend to arthroscopic knee procedures.

Hypothesis: A hyperosmolar irrigation solution used in knee arthroscopy will reduce the extent of fluid extravasation to surrounding tissue, decrease perioperative pain, and result in diminished utilization of perioperative pain medication.

3. Selection of Subjects

Inclusion Criteria: Adult patients (18 years of age or greater) undergoing arthroscopic knee surgery who are willing and able to consent.

Exclusion Criteria: Current pregnancy or breastfeeding; Unable to give consent; Prisoner; Mentally Disabled.

Sample Size: We anticipate enrolling up to 100 patients to complete the study. Patients will be evenly randomized to either hyperosmolar or standard irrigation solution.

4. Study Procedure

Timeline: 12-24 months of data collection

Protocol: Study candidates will be identified as they present to the clinic at the Missouri Orthopaedic Institute at the University of Missouri, and will be evaluated by one of our three sports orthopaedic surgeon co-investigators. Informed consent will be obtained as per IRB protocol. Enrollees will receive a copy of the study protocol, consent, and HIPAA form. Background patient information will be collected including age, sex, BMI and co-morbidities. American Society of Anesthesiologist (ASA) classification will be assigned by the involved anesthesiologist.

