Lactate Ringer's (LR, 273mOsm/L) is commonly used at our facility as our isotonic standard irrigation solution and will serve as the control to be evaluated against a hyperosmolar (1.9%, 600mOsm) solution. The hyperosmolar solution will be created by adding 120cc of 23.4% NS solution to a 3L bag of LR. The patient will be randomized before surgery by a research team member by obtaining a sealed envelope that designates the type of irrigation solution to be used in the surgery. If randomized to the hyperosmolar group, an OR staff member will make the solution prior to the start of the case. The surgeon and patient will be blinded to the type of irrigation solution used in surgery.

Quantitative variables that will be recorded include, pre and post-operative blood pressure, the type and amount (mL) of irrigation fluid used, amount of intravenous fluid used (mL), pre and post-operative weight (lb), procedures performed, number of portals, arthroscopic surgical time (minutes), pre and post-operative knee girth measurements (cm), and amount of perioperative opioid medication. We will also document any immediate, post-operative adverse effects (ie, airway comprise, prolonged intubation, etc.).

Weight: On the day of surgery, the patient's weight will be measured to the closest one tenth of a pound (lb) before and after surgery on the same calibrated, digital weighing scale. Patients will be weighed while wearing the same attire and hospital gown for each measurement. After surgery, patients will be weighed before discharge and before voiding or eating to ensure that the maximal amount of weight gain attributable to shoulder arthroscopy can be documented. A standard amount of dressing will be applied for each procedure that is surgeon specific and will be accounted for during the calculation of weight gain. Intraoperatively, we will record the

amount of intravenous fluid given during the case (mL).

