Knee Girth: Change in knee size (girth) will be evaluated based on change in surface area. Prior to start of the surgery, a sterile measuring tape will be used to record knee girth. Following the surgical procedure the operating surgeon will perform a repeat measuring of the knee girth. During the assessment, the patients will lay supine with the tester aiming to maintain the hip in neutral position. The knee will be relaxed and extended as much as possible. If the knee extends below 0°, a cylinder firm back roll will be placed under the heel of the foot. The tester will stand closest to the examined leg and place a small dot with a pen 1 cm proximal to the base of the patella using a non-elastic tape measure. The mark will be removed between measurements. The tape measure will be placed carefully and snug above the dot, and the tester will measured the knee joint circumference. The tape measure will be blinded on the side facing the tester. When the tester is satisfied with the alignment of the tape measure, the unblinded scale will be revealed to the data recorder. The value will be recorded to the nearest 0.1 cm and the measurement will be repeated. The highest value of the two knee circumference recordings will be used in the data analysis

Prior to departure from the hospital, the patient will be given the option to either receive a paper copy of the Pain Evaluation form or have an electronic version sent to them (through Patient IQ) each day. The patient will be instructed to write down their pain level (based on the Visual Analog Score, 0-10) and amount of pain medication taken during each day from the day of surgery to post-operative day 3. If given the paper form, the patient will return this form at his/her first post-operative clinic visit.

Approximately 1 year after surgery, patients will be contacted via telephone by a member of the research team. A telephone questionnaire will be conducted to gain additional information about their recovery and current functional status. The phone interview will include questions pertaining to three outcome measures: 1) KOOS Jr, 2) Single Assessment Numeric Evaluation (SANE) score for their knee, and 3) Data collection regarding any additional surgeries involving the affected shoulder.

5. Confidentiality of Data

Patient confidentiality during the course of this study will be protected in compliance with HIPAA requirements as well as the requirements of the University of Missouri Health-Sciences IRB.

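### The girth level is not carried across surgery and only the post-operative tester is named, so change in girth contains avoidable measurement error

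*Protocol*

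**What the plan says.** All of the girth procedure is in protocol section 4, Study Procedure, under Knee Girth.

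- **Baseline reading.** "Prior to start of the surgery, a sterile measuring tape will be used to record knee girth". The sentence is passive and names no tester.
- **Post-operative reading.** "Following the surgical procedure the operating surgeon will perform a repeat measuring of the knee girth".
- **Level.** The tester is to "place a small dot with a pen 1 cm proximal to the base of the patella using a non-elastic tape measure".
- **Fate of the dot.** "The mark will be removed between measurements". The text does not say which measurements.
- **Protection against steering.** "The tape measure will be blinded on the side facing the tester", and a separate recorder reads the scale.
- **Value kept.** "The highest value of the two knee circumference recordings will be used in the data analysis".

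Elsewhere in section 4, study candidates "will be evaluated by one of our three sports orthopaedic surgeon co-investigators", so the operating surgeon is presumably one of three. On masking, "The surgeon and patient will be blinded to the type of irrigation solution used in surgery".

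No sentence carries the dot, or a record of its position, from the pre-operative to the post-operative session. None requires the same person to measure at both times.

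**The concern.** The quantity of interest is a within-patient change in circumference. It is cleanest when both circumferences are taken at one level by one person. Circumference varies along the limb, so an error in level becomes an error in girth. Here the level has to be found again after surgery, on a knee that irrigation fluid may have distended. If someone else took the baseline reading, a difference in technique between the two people also enters the change score.

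The protocol applies a stricter standard to its other physical measure. The Weight paragraph requires one scale and the same clothing before and after surgery. Girth has no matching safeguard for level or tester.

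At stake is precision on the first objective, fluid extravasation, in a trial of up to 100 patients. An analysis plan could not repair this, because a level that was not preserved cannot be recovered from the data.

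**Working it through.** **Step 1: does the gap depend on how the sentence about the dot is read?**

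- If removal is between sessions, the level is erased before the post-operative reading.
- If removal is between the two repeats of a session, each repeat gets a fresh dot. That is a sound way to keep repeats independent, but still nothing preserves the level until after surgery.

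The gap is the same either way. The reading affects only the size of the error.

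**Step 2: inputs.** From the protocol: up to 100 patients, evenly randomised (50 per arm), and the higher of two readings kept. The protocol gives no SD, effect size, power or reliability figure for girth, so there is no figure of its own to reproduce. The following are assumptions:

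- SD of the error in level: 0.5 cm
- change in circumference per cm of limb: 0.5 to 1.0 cm
- SD of true girth change: 1 to 2 cm

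The relocation SD in girth is therefore 0.5 × 0.5 = 0.25 cm to 0.5 × 1.0 = 0.5 cm. Let r be that SD divided by the true-change SD. It runs from 0.25/2 = 0.125 to 0.5/1 = 0.5.

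**Step 3: added variance of the change score.**

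- Relocated once per session: added fraction = 2r². Low: 2 × 0.125² = 3.1%. High: 2 × 0.5² = 50%.
- Dot re-placed for each reading, higher kept: the variance of the larger of two independent normal errors is (1 − 1/π) = 0.682 of a single error's variance. The added fraction is 2 × 0.682 × r². Low: 2.1%. High: 34%.

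The loss in effective sample size is 1 − 1/(1 + added fraction). This is 3% to 33% in the first case and 2% to 25% in the second, so about 2 to 33 of 100 patients overall.

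**Step 4: what this does to power.** With 50 per arm, two-sided alpha 0.05 and no added error, 80% power corresponds to a difference of (1.960 + 0.842) × √(2/50) = 0.56 true-change SDs. Power for that same difference:

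| r | Once per session | Each reading, higher kept |
|---|---|---|
| 0 | 80% | 80% |
| 0.125 | 79% | 79% |
| 0.25 | 75% | 77% |
| 0.5 | 63% | 68% |

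The r = 0.125 row follows from Φ(2.802/√1.031 − 1.960) and Φ(2.802/√1.021 − 1.960).

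**Step 5: different testers.** If the pre- and post-operative testers differ and their offsets vary independently from patient to patient with SD t, in units of the true-change SD, a term 2t² is added. With t = 0.25, the each-reading powers of 77% and 68% become 72% and 64%.

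**Step 6: is the comparison between arms biased?** A simulation of 20,000 trials used r = 0.5, the higher of two readings and a constant post-operative tester offset of 0.4. Mean change in the control arm was 1.90 against a true 1.50. The difference between arms was 0.559 against a true 0.560, type I error was 4.9%, and power was 67%. The offset distorts the change within each arm but cancels between arms. The upward shift from keeping the higher reading cancels between sessions.

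**The case against.** The strongest case against is that the plan has a reproducible rule. It uses a fixed distance from a bony landmark, a standard leg position, two readings, a tape hidden from the tester and a separate recorder. The same paragraph uses the word measurement for a single reading that is then repeated, so the dot sentence may govern only repeats within a session, where removal is good practice. A repeat measuring by the surgeon may imply that the surgeon also took the baseline. Inked skin may itself move as the knee swells. Weight is recorded too and has no relocation error.

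Most of this stands as a limit on the point. It does not close the gap, because the plan neither preserves the level across surgery nor names the baseline tester.

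A reader might infer four stronger things that the document does not support:

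- *The dot is ordered to be erased between sessions.* The sentence is ambiguous.
- *The testers differ.* The baseline tester is only unnamed.
- *The treatment comparison is biased.* Allocation is randomised and the surgeon is blinded, so the error should be alike in both arms. Bias would need an error that depends on arm, for example relocation error that grows with swelling. That is conceivable, but nothing in the document shows it.
- *The first objective rests on girth alone.* Weight serves it too, and neither measure is designated as primary.

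**Conclusion.** The point holds as a loss of precision. As written, change in girth contains relocation error that could be avoided, and tester error if the testers differ. The difference between arms is not biased by this alone, although the absolute change within each arm can be shifted.

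The size cannot be taken from the document. Under the assumptions stated, added variance is roughly 2% to 50%. The low end costs about one point of power and is negligible; the high end would matter with up to 100 patients. A middle case (gradient 0.75, true-change SD 1.5 cm, so r = 0.25) adds 8.5% if each reading is re-marked and 12.5% if relocation happens once per session. These figures exclude any tester difference.

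This is a cheap improvement, not a flaw that invalidates the outcome.

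**What to change.** Amend the Knee Girth paragraph in three ways:

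1. State that dot removal applies only between the two repeats of the pre-operative session.
2. After that pair, ink the level with a skin marker that survives skin preparation, and place the post-operative tape at that line. If the mark is lost, find the landmark again and record that this happened.
3. Require the same tester, the blinded operating surgeon, at both times.

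The hidden tape and separate recorder stay, and continue to keep the tester from steering towards the earlier value.

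The cost is a few sentences and a skin marker, with no extra staff. There are three drawbacks. The mark must survive skin preparation; the plan specifies a sterile tape at baseline but does not say whether that reading comes before or after preparation. The skin may shift slightly as the knee swells. The two post-operative repeats will share one level, so they no longer average over its placement.

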Safety and Efficacy of Hyperosmolar Saline Irrigation Fluid in Arthroscopic Knee Surgery

IRB Project #: 2011296

PROTOCOL VERSION NUMBER: 3.0

DATE: 03 APR 2019

Principal Investigator: [name]

Co-Investigators: [name], DVM, PHD; [name]; [name]

Study Sites: University of Missouri Health System

TABLE OF CONTENTS

1. Background Information & Significance
2. Objectives, Contribution, & Hypothesis
3. Selection of Subjects
4. Study Procedure
5. Confidentiality of Data
6. Assessment of Risks & Benefits
7. Payment and Remuneration, and Costs
8. References

1. Background Information & Significance

An isotonic solution, such as saline (0.9%, 300mOsm/L) or lactated ringer's (273 mOsm/L), is commonly used and safely proven for joint irrigation during arthroscopy. Arthroscopic fluid is usually pressurized to enable visualization through dilation of the joint or bursa and prevent bleeding from the microvasculature. It has been recommended that this pressure be maintained at 49mmHg or less below the systolic blood pressure to preserve the clarity of view. The combination of large amounts of pressurized irrigation solution and lengthy arthroscopic procedures may cause substantial tissue fluid retention. Thus, extravasation of irrigation fluid into the periarticular tissues is inevitable and may create technical difficulties as well as patient morbidity and complications. Previous investigators have reported complications including tracheal obstruction, post-operative airway edema and compromise leading to prolonged intubation, excess weight gain, neurologic injuries, skin necrosis, and fluid overload associated with excessive fluid extravasation and tissue retention. Furthermore, it has been shown that fluid accumulated during the operation is slowly released back into the systemic circulation. Although there is not a rapid change in circulating volume, there may be implications for elderly patients and those with multiple comorbidities during prolonged arthroscopic surgery. Our research team and other groups have reported that hyperosmolar solutions (up to 600 mOsm/L) are chondroprotective *in vitro*, and safe and effective clinically when used as the irrigation solution for arthroscopic shoulder surgeries in a prospective controlled randomized clinical trial.

2. Objectives, Contribution, & Hypothesis

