All subjects will be assigned a study identification number that requires the use of a key in order to decipher a subject's personal identification information. The key will be kept in the Cerner Power Trials database, which is password protected. The study identification number will be used to label all paper data collection instruments.

All subject information in electronic format will be kept in password-protected storage. All subject information in paper format will be kept in locked cabinets in a secured suite at the

Missouri Orthopedic Institute, and otherwise will be archived in a secure storage facility, or destroyed.

6. Assessment of Risks & Benefits

Risks: Risks for breach of confidentiality does exist but will be limited with tight control and limited access to the investigators.

Benefits: The potential benefits of this study lie in determining the differences noted in our shoulder arthroscopy clinical trial extend to arthroscopic knee procedures.

Data Safety Monitoring Plan: Subject safety will be ensured through standard of care perioperative monitoring by the anesthesia staff.

7. Payment and Remuneration, and Costs

Payment and Remuneration: Participants will not receive payment for participating in this study.

Costs: Subjects will be responsible for the cost of any surgical and clinic follow up costs. The treatment arm does not in any way effect the costs that patients are experiencing.

8. References

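### The 1-year outcomes have the telephone as their only route, and the re-operation item names the shoulder in a knee trial

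*Protocol*

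**What the plan says.** Protocol section 4 (Study Procedure) sets the long-term follow-up in one short paragraph: "Approximately 1 year after surgery, patients will be contacted via telephone by a member of the research team". The content follows: "The phone interview will include questions pertaining to three outcome measures: 1) KOOS Jr, 2) Single Assessment Numeric Evaluation (SANE) score for their knee", and, as the third item, "Data collection regarding any additional surgeries involving the affected shoulder". The paragraph gives no second route, number of call attempts, time window or record check. It presents the call as a way to learn more about recovery and function.

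Three other places bear on this:

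- **Electronic route.** The preceding paragraph of section 4 lets patients choose a paper pain form or "have an electronic version sent to them (through Patient IQ) each day". This covers the day of surgery to post-operative day 3.
- **Site and records.** The title page gives one health system: "Study Sites: University of Missouri Health System". Section 5 mentions a Cerner product only as the place for the identification key: "The key will be kept in the Cerner Power Trials database, which is password protected". The medical record is not named as a source of outcome data.
- **Size and aims.** Section 3 states "We anticipate enrolling up to 100 patients to complete the study", split evenly between the arms. The objectives and hypothesis in section 2 concern fluid extravasation, pain and pain medication. Function and re-operation at 1 year appear in neither.

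**The concern.** All three 1-year items depend on reaching the patient by one mode. If those who cannot be reached differ in outcome from those who can, for example because they have recovered or were treated elsewhere, the patients left may not represent their arm. If this differs between arms, the comparison is biased, and no adjustment of the standard error shows it. The loss of precision is the smaller problem.

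Additional surgery deserves the most care. Beyond the immediate post-operative adverse effects in section 4, it is the only later safety-type event that the protocol names, and monitoring in section 6 is perioperative. In a trial of this size, a few unknown statuses could change the comparison of a rare event.

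The item also asks about the wrong joint. If the interview script follows the protocol text, even a completed call would not record an operation on the study knee.

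**Working it through.** **1. Routes, side by side.**

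| 1-year item | Route written | Other route that the protocol suggests | Limit of that route |
|---|---|---|---|
| KOOS Jr, SANE | Telephone interview | Electronic form system, used for the pain diary | Named only to day 3, as an option against paper; use at 1 year not shown |
| Additional surgery | Telephone interview (worded for the shoulder) | Record of the single health system | Inferred from the site, not named as a source; misses operations elsewhere |

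The record cannot supply KOOS Jr or SANE. The electronic form could supply them, because both are patient-reported.

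**2. The protocol's own figure.** There is none to reproduce. No alpha, power, target difference, SD or loss rate is given for the 1-year outcomes, and no derivation is given for the 100 patients.

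**3. Illustration of the gain from a second route.** From the protocol: at most 100 patients, evenly allocated, so at most 50 per arm. Assumed: two-sided 5% level, 80% power, equal loss in both arms, 20% or 40% missed by telephone, and half of those missed recovered by the second route.

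Detectable difference in SD units (normal approximation) = (1.960 + 0.842) × √(2/n per arm).

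- No loss, n = 50: 2.802 × √(2/50) = 0.56.
- 20% missed, n = 50 × 0.80 = 40: 2.802 × √(2/40) = 0.63. With half recovered, n = 45: 2.802 × √(2/45) = 0.59.
- 40% missed, n = 50 × 0.60 = 30: 2.802 × √(2/30) = 0.72. With half recovered, n = 40: 0.63.

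Power for 0.56 SD, the difference that 50 per arm would detect with 80% power:

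| Missed by telephone | Telephone only | Half of missed recovered |
|---|---|---|
| 20% | 71% | 76% |
| 40% | 58% | 71% |

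An exact two-sample t calculation gives slightly larger detectable differences (0.566, 0.634 and 0.736 SD at 50, 40 and 30 per arm) and the same picture.

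**4. Re-operation.** Under the same assumed losses, 50 × 0.20 = 10 or 50 × 0.40 = 20 patients per arm would have unknown status. A record search would find operations done within the health system for these patients. How many of their operations would be done elsewhere cannot be told from the protocol.

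**The case against.** The strongest reply is that nothing here spoils a result that the trial sets out to give. The 1-year items serve no stated objective, and no 1-year comparison is specified. A telephone interview is a workable way to collect two short scores and a surgical history. This stands, and it limits the priority.

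Four stronger readings are tempting, and the protocol does not support them:

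- **A single missed call loses the patient.** The text fixes the mode, not the number of attempts. Repeat calls are compatible with it.
- **The hospital record would fill most of the gaps.** The record is an inference from the single-system site. It misses operations elsewhere, and for an unreached patient no entry does not mean no re-operation.
- **The electronic system is ready for use at 1 year.** It is shown only as an option for the pain form to day 3. Its reach for patients who chose paper is unknown.
- **The loss is the whole gap to complete follow-up.** Set against full response, 20% or 40% non-response raises standard errors by 12% (1/√0.80) or 29% (1/√0.60). No second route would recover everyone, so the fair measure is the gain under partial recovery, and at 20% missed that is only about 0.04 SD.

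A statistical analysis plan that is not shown may deal with missing values. That does not answer the point: it can say how missing data are analysed, but it cannot create a second way of collecting them.

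**Conclusion.** The point holds in a limited form. The telephone is the only written mode for all three 1-year outcomes, although the same section already uses an electronic patient-reported route. Patients who cannot be reached by telephone contribute nothing at 1 year, and additional surgery depends on patient report alone. The shoulder wording is the firmest part because it is an error on the face of the text. Its effect depends on the interview script, which is not at hand, so it cannot be said that knee re-operations will in fact be missed.

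The size of the problem is unknown because the protocol gives no response rate. The illustrative gain from a second route is 0.04 SD in detectable difference at 20% missed (0.63 to 0.59) and about 0.10 SD at 40% missed (0.723 to 0.626). It assumes equal loss in both arms and recovery of half of those missed, and it says nothing about bias. The priority is low to moderate, and the pain, extravasation and medication results are untouched.

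**What to change.** 1. Keep the telephone call. Offer KOOS Jr and SANE electronically to patients not reached by telephone, once use of the existing system at 1 year is confirmed. Record the mode for each score.
2. For every patient in both arms, reached or not, check the health-system record for later surgery on the study knee. Use the patient's answer to add operations done elsewhere. Report that outside operations in unreached patients remain unknown.
3. Change the joint in the additional-surgery item from the shoulder to the study knee, in the protocol and in the interview script if it carries the same wording.

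The cost is one electronic form and a record search for at most 100 patients, which can also be done retrospectively. The downsides are real: the two scores will come from mixed modes, and recording the mode documents that difference without removing it. Re-operation will be ascertained more fully in reached than in unreached patients, because the record covers one health system only.

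### The third 1-year outcome measure asks about surgery on the shoulder in a knee-only trial; correct it to the operated knee and check the telephone questionnaire

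*Protocol*

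**What the plan says.** The 1-year follow-up is described in the last paragraph of Protocol section 4. A member of the research team telephones the patient about a year after surgery and works through a questionnaire. The Protocol states: "The phone interview will include questions pertaining to three outcome measures". It then lists them:

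1. KOOS Jr;
2. the "Single Assessment Numeric Evaluation (SANE) score for their knee";
3. "Data collection regarding any additional surgeries involving the affected shoulder".

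The rest of the Protocol concerns the knee. The title is "Safety and Efficacy of Hyperosmolar Saline Irrigation Fluid in Arthroscopic Knee Surgery". The inclusion criterion in section 3 admits adults "undergoing arthroscopic knee surgery who are willing and able to consent". The objectives and hypothesis in section 2 and the girth measurement in section 4 are also about the knee.

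The shoulder does have a legitimate place in the document. The team's earlier trial was in shoulder arthroscopy, and sections 2 and 6 give the contribution of this study as "determining the differences noted in our shoulder arthroscopy clinical trial extend to arthroscopic knee procedures". That is a separate study, and nothing in this Protocol enrols shoulder patients.

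**The concern.** The phrase is not background. It defines one of the outcome measures, so it instructs the person who writes or reads the telephone questionnaire. Followed to the letter, the interviewer would ask a knee patient about operations on a shoulder that was never part of the study, and would not ask about repeat surgery on the knee that was irrigated.

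The trial's title promises safety as well as efficacy, and this item is the only one in the Protocol that would record a surgical event after the immediate post-operative period. If the wrong joint is asked about at the single 1-year call, re-operation on the study knee would have to be recovered by some route the Protocol does not describe.

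**Working it through.** There is no sample size, power or event count behind this point, so no formula applies. The check compares the text and makes two simple counts.

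**Step 1. Which joint does each part of the Protocol name?**

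| Place in the Protocol | Joint |
|---|---|
| Title | Knee |
| Section 2, objectives and hypothesis | Knee |
| Section 3, inclusion criterion | Knee |
| Section 4, girth measurement | Knee |
| Section 4, 1-year call, SANE item | Knee |
| Section 4, 1-year call, additional surgeries | Shoulder |

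The last two rows come from the same sentence. No participant has an affected shoulder under this Protocol, so the last row cannot be read as a deliberate choice.

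**Step 2. Is the slip isolated, and does it change what is measured?** The word shoulder occurs 5 times in sections 1 to 7, leaving out the reference list:

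| Place | Use | Correct here? |
|---|---|---|
| Section 1, background | Earlier randomized shoulder trial | Yes |
| Section 2, contribution | The team's shoulder trial | Yes |
| Section 4, weight procedure | Weight gain attributed to shoulder arthroscopy | No |
| Section 4, 1-year call | Additional surgeries | No |
| Section 6, benefits | The team's shoulder trial | Yes |

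So 3 uses are correct and 5 − 3 = 2 are misplaced. The one in the weight paragraph, "maximal amount of weight gain attributable to shoulder arthroscopy can be documented", gives the reason for weighing the patient before voiding or eating. The weighing is done the same way whichever joint is named, so no measurement changes. Only the one in the 1-year item determines what is collected.

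**Step 3. Is later surgery on the study knee collected anywhere else?**

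- Adverse effects (section 4): "We will also document any immediate, post-operative adverse effects". This covers the immediate period only.
- Pain form (section 4): from the day of surgery to post-operative day 3, covering pain level and medication.
- First post-operative clinic visit (section 4): mentioned only as the occasion for returning the paper pain form. No re-operation question is specified.
- Data safety monitoring plan (section 6): perioperative monitoring by anesthesia staff.

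None of these reaches re-operation on the knee. The 1-year item is the only stated source.

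**Step 4. What share of the 1-year outcomes is affected?** 1 of 3. The number of patients affected cannot be given, because it depends on how the questionnaire is worded, and the questionnaire is not shown.

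**The case against.** The strongest reply is that nobody could misunderstand the sentence. Everything around it is about the knee, the literal reading points to a joint that no participant had treated, and an interviewer telephoning a knee patient would probably correct it without thinking. A true contradiction leaves staff with two workable instructions; this leaves one. Further, additional surgery appears in none of the objectives or the hypothesis, the call is meant to gather supplementary information, and any loss of data depends on a questionnaire that cannot be seen.

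Much of this stands. The intended joint can be inferred, the stated objectives are unaffected, and no loss of data has been shown. The 1-year call is also not the only contact after discharge, since a clinic visit is mentioned; it is only the one contact at which the Protocol plans to ask about further surgery.

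What does not follow is that the text may be left alone. A questionnaire is often drafted from the protocol's wording, and two stray shoulder references in the same section suggest that text was carried over from the earlier trial. That origin is an inference and nothing here depends on it, but it is a reason to look at the questionnaire. Section 4 also says that enrollees receive a copy of the protocol, so participants would read the wrong joint as well. Nor would a statistical analysis plan, if one exists, normally correct which joint an interview asks about.

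**Conclusion.** The point holds. The Protocol names the wrong joint in 1 of its 3 outcome measures at 1 year, in text that defines what is collected, and no other section makes good the omission. This is certain from the wording alone.

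The consequence is conditional. If the questionnaire repeats the phrase and is read as written, re-operation on the study knee is not captured. If the questionnaire already says knee, only the Protocol text is wrong. In either case the extravasation, pain and pain-medication objectives are unaffected. The correction should be made because the phrase specifies data and the remedy is very cheap, not because any loss has been demonstrated.

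**What to change.** In the 1-year paragraph of section 4, change the third item so that it refers to additional surgery on the operated (study) knee. Index knee would serve equally well, although neither is yet a defined term in the Protocol. Before the questionnaire is used, confirm that its question names the same joint.

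As tidying in the same revision, change shoulder to knee in the weight paragraph of section 4. The references to the earlier shoulder trial in sections 1, 2 and 6 are correct and should stay.

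The cost is one phrase in the Protocol and one check of the questionnaire. No visit, question or burden on patients is added.
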